1. GENERAL QUESTIONS

Protocol Number **IRB-300009227**

Principal Investigator Name **[name]**

Title of proposed project:

Continuous Glucose Monitoring (CGM) in Kidney-Transplanted Adults

* Select the type of application you are submitting to the IRB for review. **Initial Application**

NOTE: The ePortfolio should NOT be used for submitting Reliance Agreements, Expanded Access (including emergency use), or Humanitarian Use Device applications.

For Reliance Agreements, submit a copy of the Institution Review Form.

For Expanded Access and HUD submissions, submit a copy of the Human Subjects Protocol.

Initial IRB Protocol Application

* **PURPOSE:** In non-technical, lay language, provide the purpose of the project. The contents of this section are copied to other areas of IRAP. As such, provide **only** the purpose of the project here.

The purpose of this study is to determine the feasibility and acceptance of continuous glucose monitoring (CGM) in adults with diabetes who underwent kidney transplantation compared to those who use glucometers, and to determine whether CGM improves Post-Transplant Hyperglycemia, microalbuminuria and subclinical rejection rates in kidney transplant patients, as compared with those who use glucometers.

BACKGROUND: In 2-3 paragraphs, summarize the past experimental/clinical findings leading to the design of this project. Include any past or current research that informed the study design and any previous results that are relevant to understanding the project. Lastly, list the study outcomes that will be measured to evaluate the purpose of the project. It is not necessary to include methodology in this section. NOTE: Technical terms must be defined in simple language. Abbreviations must be spelled out. Provide references for any specific citations.

The proposed study will address a current diabetes disparity in adults with low socio-economic status who underwent kidney transplant (KT) at UAB. During the last three years, over 1000 kidney transplants have been performed at the UAB Comprehensive Transplant Institute; however, according to our internal statistics, around 70% of our patients do not have access to advanced diabetes technology due to limited insurance coverage, making post-transplantation glucose monitoring challenging, and contributing to disparate outcomes for low-income patients, including possibly kidney allograft rejection rates.

Recent data has suggested that social determinants of health defined as the conditions in which individuals live and work such as poverty, unemployment, inability to pay for medications, public health insurance and lower education level can adversely impact kidney graft survival (15,16,17,18). However, despite increased awareness of kidney-related health disparities in low-income and minority populations, outcomes data specific to post-kidney transplantation remain sparse.

UAB Hospital is the major transplantation referral center in the southeast area. According to our last three years statistics, nearly 70% of patients who underwent KT at the UAB Kidney Diabetes Clinic are low-income and African Americans who are publicly insured.

The gold standard for glucose monitoring is the use of a glucometer (glucose meter). To use most blood glucose meters, a test strip is placed into the device. Then with a special needle, one pokes a clean fingertip to get a drop of blood. One then carefully touch the test strip to the blood and waits for a blood glucose reading to appear on the screen of the meter.

Continuous glucose monitors have been developed to take the pain of fingertip sticks out of the process of glucose monitoring, as this is a reason for noncompliance among those who are recommended to use a glucometer. A continuous glucose monitor uses a sensor placed under the skin to measure blood sugar level, transmits each reading to a smartphone, smartwatch or small recording device worn on the patient's body, and gives an alert when blood sugar levels are too low or too high.

Because continuous glucose monitoring (CGM) is either not covered by public insurance or incurs high out-of-pocket costs (19), the majority of these patients have no access to advanced diabetes technology, making Post-Transplant Hyperglycemia (PTRH) monitoring a challenge. The glucose management in post-transplant patients is unique due to the need for high doses of steroids and immunosuppressants, variations in kidney function, frequent gastric symptoms, and the presence of cardiovascular comorbidities. Lack of public health insurance coverage for CGM in this setting is largely driven by a dearth of rigorous data demonstrating improved health outcomes for low-income post-transplant patients when using CGM. The objective of this pilot study is to test for feasibility and acceptability of CGM in low income patients with diabetes who have undergone kidney transplantation. If successful, we will use the pilot data as the foundation for a larger well-powered trial to examine whether CGM improves PTRH and kidney graft survival. At this moment, access to CGM is largely relegated to patients with private insurance. We have designed this study in order to address the disparities in access to advanced diabetes technology, thereby promoting health equity in post-kidney transplant outcomes

The use of continuous glucose monitoring (CGM) compared with blood glucose meter monitoring in non-transplant patients with diabetes resulted in lower HbA1C by 0.4 to 0.5% within the first three months of use without major changes in patients' antidiabetic regimen, possibly due to patients becoming more conscious about their diabetes status and diet (10,11). CGM free style libre-2 measures the interstitial fluid every minute with glucose sensors being replaced every two weeks (12). To our knowledge there are no studies that assess the role of CGM in improving glycemic and transplant outcomes in solid organ transplant patients, mainly because access to CGM is often limited by inadequate health insurance coverage or high out-of-pocket costs.

METHODS: Describe the procedures for all aspects of your protocol. Tell us what you are doing.

A cross-over design will allow estimation of feasibility and acceptability of patients using CGM vs patients using blood glucose meter monitoring (conventional therapy). The study will consist of two phases. Phase I will last 3 months, followed by a 2 month washout period, before the beginning Phase II, which will also last 3 months (for a total of 8 months).

Note: Standard of Care for post-kidney transplant patients

Patients who receive kidney transplants at UAB return to the Kidney Transplant Clinic every two weeks for the first year after transplant to have routine exams and bloodwork drawn, to insure that their body will not reject the donor organ. We intend to schedule any study-related procedures during these routine clinic visits so that participants will not have to return to the clinic on a more frequent basis than they would for their routine post-op care.

We will not draw research only bloodwork during these visits. We will collect data from standard of care procedures that would happen for the patient, whether they were in the research study or not - this includes data from their glucometer readings, their kidney biopsy at Month 5/6, and data from the visits that are recorded in their medical record.

Note: CGMs

The Freestyle Libre 2 CGM system consists of a sensor and a reader. The sensor will be inserted into the participant's shoulder during their respective treatment phase by the study coordinator. The sensor is designed to be removed and replaced every two weeks while it is being used. The reader is a device that reads the information from the sensor. Please see Instructions for Use (IFU) directions that are included in the Device section for more details about the placement and removal of the sensor. Participants will be given the IFU for the CGM system at the time of sensor placement.

Participants will be able to utilize the provided reader or a smartphone app that is part of the Freestyle Libre 2 CGM system to follow their glucose readings in real time, to assist with their diabetes management.

As a control measure, we will have participants in the control phase wear the Freestyle Libre Pro for a two-week period at the beginning and end of their control phase of the study. The sensor is similar to the Freestyle Libre 2. When the sensors are removed, they will be discarded. The Freestyle Pro does not have an end user reader or smartphone app; only a healthcare professional can receive the data collected/recorded by the CGM sensor. This can (and will) be collected remotely, so that participants need not return the sensors to the study site, but can discard them as they would per the IFU.

Participants will be approached about enrollment following their kidney transplant while they are still in the hospital. If they agree to enroll, their medical record will be reviewed for history, diagnosis, and demographic information.

At baseline, participants will then be randomized into one of two arms: **Group 1**, which will receive the Freestyle Libre 2 CGM in Phase I or **Group 2**, which will be provided with glucometers, the standard of care method of glucose monitoring, in Phase I.

Each group will have 15 total participants.

Please find attached in Section 31 a Schedule of Events to assist with clarity of study flow.

Baseline Visit (Week 0)

- **For participants in Group 1 only:** participants will be fitted with a Freestyle Libre 2 continuous glucose monitor. A sensor will be inserted in their shoulder for this device. They will be given instructions on how to use the reader that is provided with the sensor to obtain your blood sugar readings. They will also be given instructions on how to change the sensors. They will be given the instructions for using the device that are provided by the device manufacturer.
- **For participants in Group 2 only:** Participants will receive a glucometer (glucose monitor) to check and record daily blood sugar readings, which they will be asked to do this three times a day, before meals. Participants will be fitted with a Freestyle Libre Pro continuous glucose monitor, which they will be asked to wear for two weeks. At the end of the two weeks, the participant will remove the Freestyle Libre Pro sensor and discard it at home. Data will be collected remotely from the Libre Pro system.
- **For participants in both Group 1 and Group 2:** medical record will be reviewed for information about diabetes, including lab work that was collected as part of standard of care. We will not collect lab work for research purposes only. Con meds and adverse events will be collected. Participants will be asked to complete 2 questionnaires, the Diabetes Treatment Satisfaction Questionnaire (DTSQ) and the Hypoglycemic Confidence Scale (HCS)

Phase I: Week 2 (Visit 2)

- **For participants in both Group 1 and Group 2:** medical record will be reviewed for information about diabetes, including lab work that was collected as part of standard of care. We will not collect lab work for research purposes only. Con meds and adverse events will be collected. Participants will be asked to complete the DTSQ and the HCS
- **For participants in Group 1 only:** obtain readings from the CGM from the time that it was initially inserted
- **For participants in Group 2 only:** participants will be fitted with a Freestyle Libre Pro continuous glucose monitor, which they will be asked to wear for two weeks. At the end of the two weeks, the participant will remove the Freestyle Libre Pro sensor and discard it at home. Data will be collected remotely from the Libre Pro system.

Phase I: Week 12 (Visit 3)

- **For participants in both Group 1 and Group 2:** medical record will be reviewed for information about diabetes, including lab work that was collected as part of standard of care. We will not collect lab work for research purposes only. Con meds and adverse events will be collected. Participants will be asked to complete the DTSQ and the HCS
- **For participants in Group 1 only:** participants will remove the Freestyle Libre 2 sensor and discard it. Participants will be given a glucometer to continue to monitor glucose levels.
- **For participants in Group 2 only:** participants will be fitted with a Freestyle Libre Pro continuous glucose monitor, which they will be asked to wear for two weeks. At the end of the two weeks, the participant will the Freestyle Libre Pro sensor and discard it at home. Data will be collected remotely from the Libre Pro system.

Washout period (Weeks 13-19)

A two month washout period will start at the end of Phase I, during which all participants, regardless of Group assignment, will use glucometers to monitor blood glucose levels.

After the washout period, participants will cross into the other arm of the study - those in Group 1 will continue using the glucometers, while those in Group 2 will receive the Freestyle Libre 2 CGM.

Phase II: Week 20 (Visit 4)

- **For participants in both Group 1 and Group 2:** medical record will be reviewed for information about diabetes, including lab work that was collected as part of standard of care, as well as data from the kidney biopsy generally performed at post-operative month 5 or 6. We will not collect lab work or complete biopsies for research purposes only. Con meds and adverse events will be collected. Participants will be asked to complete 2 questionnaires, the DTSQ and the HCS
- **For participants in Group 1 only:** participants will be fitted with a Freestyle Libre Pro continuous glucose monitor, which they will be asked to wear for two weeks. At the end of the two weeks, the participant will the Freestyle Libre Pro sensor and discard it at home. Data will be collected remotely from the Libre Pro system.
- **For participants in Group 2 only:** the Freestyle Libre-2 CGM will be inserted at this clinic visit by the study coordinator. Participants will be given the Instructions for Use (IFU) for the CGM at this time.

Phase II: Week 32 (Visit 5) - End of Study

- **For participants in both Group 1 and Group 2:** medical record will be reviewed for information about diabetes, including lab work that was collected as part of standard of care. We will not collect lab work for research purposes only. Con meds and adverse events will be collected. Participants will be asked to complete 2 questionnaires, the DTSQ and the HCS
- **For participants in Group 1 only:** participants will be fitted with a Freestyle Libre Pro continuous glucose monitor, which they will be asked to wear for two weeks. At the end of the two weeks, the participant will the Freestyle Libre Pro sensor and discard it at home. Data will be collected remotely from the Libre Pro system.
- **For participants in Group 2 only:** participants will remove the Freestyle Libre 2 sensor and discard it. Participants will be given a glucometer to continue to

monitor glucose levels.

REQUIRED - SELECT ONE OR BOTH: Will this be a retrospective study and/or a prospective study?

Yes No * Retrospective

Yes No * Prospective

Yes No * Will the study involve the [prospective](#) collection or analysis of data, documents, or records?

Yes No * Will the study involve the [prospective](#) collection or analysis of biospecimens?

What is the expected end date of the study (including data analysis)?

* Provide the total number of subjects to be included at all sites, both retrospectively (including records) and prospectively.

* Provide the total number of subjects to be included at UAB, both retrospectively (including records) and prospectively.

Select the type of research.

Biomedical (non-oncology)

Behavioral (non-oncology)

Oncology

Select the status of the Principal Investigator.

Faculty/Staff

Student/Trainee

Yes No Are any of the investigators listed on the IRB Personnel Form students using this research for their capstone project, thesis, or dissertation?

Yes No Is the project to be conducted internationally?

Methodology

Select all study procedures and indicate whether the procedures are research only or routine.

Procedure	Select whether the procedure is research or routine.
Record review (which may include PHI)	Protocol Driven
Devices	Protocol Driven
Surveys, questionnaires, or interviews (one-on-one)	Protocol Driven

Yes No Does the protocol involve any procedures not described in the above table?

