Eligible participants will engage study staff during regularly scheduled, standard of care, visits. The first (i.e. baseline) visit is one day post-operative surgery. Participants will be randomized to one of two groups. Group 1 participants (n=15) will receive a Freestyle Libre continuous glucose monitor (CGM) that reports glucose levels to participants every 15 minutes for twelve weeks. Group 2 participants (n=15) will receive a glucometer for self-management of their diabetes as per the standard of care for twelve weeks. Halfway through the study (week 12 post-operative surgery), all participants will use a glucometer to manage their diabetes eight weeks, which serves as a washout period. At week 20 post-operative surgery, Group 2 participants will receive a CGM to use for twelve weeks, and Group 1 will continue using a glucometer for twelve weeks. The study will conclude at week 32 post-operative surgery visit.

Participants managing their diabetes with glucometers during the first and last twelve weeks of the study (Groups 2 and 1 respectively) as well as Group 2 during weeks 18-20 of the study will use a Freestyle Libre "Pro" CGM, which collects glucose information in the same manner as the CGM described above but reporting not provided to participants and is accessible to the study team via remote monitoring.

At regularly scheduled post-operative visits on weeks 2, 12, 20 and 32, the study team will request participants to complete two quality-of-life surveys (Diabetes Treatment Satisfaction Questionnaire (DSTQ) and Hypoglycemic Confidence Scale (HCS)) and record glucose readings from the CGM and/or glucometers. Participants' medical records will be leveraged to assess surgical outcomes, diabetes management and related clinical information (e.g. clinical labs, kidney biopsies).

Potential Risks:

Glucose monitoring related pain, discomfort and Infection: Sensor insertion and finger-prick based glucose readings may cause temporary pain, bleeding and/or bruising at the site of insertion. Moderate to severe itching, reddening and/or scaling of the skin, rash and/or bleeding are infrequent risks associated with wearing the sensor. A infrequent risk is sensor breakage, which can require sensor tip extraction via tweezer.

Group Assignment: Participants are assigned to a group by chance, which may prove to be less effective or have more side effects than the other study group or alternatives.

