All components of the device will be stored securely (behind a locked door) in the principal investigator's office in [name]. All floors above 6 in FOT are badge-protected. Only qualified research staff will have access to the office where the devices are stored. The devices will be inserted for two weeks at the beginning and end of Phase I or Phase II, dependent on group assignment. The participation will only wear the sensor for the Pro version of the device and data will be collected remotely from the device. Participants will be instructed to discard the sensor after each two week period of monitoring is complete.

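### The masked-sensor schedules do not agree, and on the dated visits the last two weeks of each control phase have no masked glucose data

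*Combined protocol and SAP*

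**What the plan says.** Three parts of the combined document describe when the masked sensor is worn.

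- **Methods narrative (1. General Questions, note on CGMs) and the device-availability section.** As a control measure, participants are to "wear the Freestyle Libre Pro for a two-week period at the beginning and end of their control phase of the study". The device section agrees: "The devices will be inserted for two weeks at the beginning and end of Phase I or Phase II, dependent on group assignment".
- **Dated visit list (Methods).** Group 2 is fitted at weeks 0, 2 and 12, and Group 1 at weeks 20 and 32. Each fitting is for two weeks: "participants will be fitted with a Freestyle Libre Pro continuous glucose monitor, which they will be asked to wear for two weeks".
- **Protection of Human Subjects, study procedures.** The wearers are "Participants managing their diabetes with glucometers during the first and last twelve weeks of the study" (Group 2, then Group 1), "as well as Group 2 during weeks 18-20 of the study will use a Freestyle Libre" Pro. The visit list has no Group 2 fitting for weeks 18-20.

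The end points are also stated. The washout begins when Phase I ends, although its heading reads weeks 13 to 19. For the trial as a whole, "The study will conclude at week 32 post-operative surgery visit", and the last visit is headed "Phase II: Week 32 (Visit 5) - End of Study". At week 12 (Group 1) and week 32 (Group 2), "participants will remove the Freestyle Libre 2 sensor and discard it".

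Time in range is the named example of a secondary outcome and is on the data collection list. The Human Subjects section records glucose readings at the visits in weeks 2, 12, 20 and 32. No visible passage says which weeks are compared between treatments.

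**The concern.** The masked sensor is the plan's own means of measuring time in range under glucometer management. A sensor records forward from its fitting, so one fitted at the closing visit of a phase records the fortnight after that phase. If sites follow the visit list, masked data exist for the opening weeks of each control phase and for a fortnight after it, but not for its end.

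Two things follow. The other group takes off its Libre 2 at the same visit, so the late windows have no concurrent comparator. The weeks with sensors in both groups then all fall within the first four weeks of a phase, when a CGM effect has had least time to build. Comparing non-matching weeks instead mixes any CGM effect with change over time since transplant. Such change is plausible: week 0 is the day after surgery, and the background section cites high-dose steroids and varying kidney function.

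**Working it through.** **Step 1: the calendar.** Control phases are weeks 0-12 (Group 2) and 20-32 (Group 1). Libre 2 is worn in weeks 0-12 (Group 1) and 20-32 (Group 2). Each Pro fitting lasts two weeks.

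| Schedule | Group 2 masked weeks | Group 1 masked weeks | Inside control phase (G2 / G1) | Closing fortnight covered |
|---|---|---|---|---|
| Narrative and device section | 0-2, 10-12 | 20-22, 30-32 | 4 / 4 | 2 of 2 each |
| Dated visits | 0-2, 2-4, 12-14 | 20-22, 32-34 | 4 / 2 | 0 of 2 each |
| Human Subjects section, if continuous wear is meant | 0-12, 18-20 | 20-32 | 12 / 12 | 2 of 2 each |

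Weeks with sensors in both groups at once:
- dated visits: 0-4 and 20-22, so 4 + 2 = 6;
- closing sensors fitted at weeks 10 and 30: 0-4, 10-12, 20-22 and 30-32, so 4 + 2 + 2 + 2 = 10.

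This step needs no assumption beyond the stated dates.

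**Step 2: illustrative bias when there is no CGM effect.** Assumed: time in range rises linearly by R = 10 to 20 points over T = 4 to 20 weeks and is then flat. Signs reverse for a fall. The estimate is the mean over the two groups of (CGM minus control).

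*Closing windows as dated.* The extreme is R = 20, T = 13.7. Rise reached, averaged over each window:
- weeks 10-12: 20 × 11/13.7 = 16.06;
- weeks 12-14: (1.7 × 20 × 12.85/13.7 + 0.3 × 20)/2 = 18.95;
- weeks 30-32 and 32-34: 20.

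Group 1: 16.06 - 20 = -3.94. Group 2: 20 - 18.95 = +1.05. Mean: (-3.94 + 1.05)/2 = **-1.44**. With R = 10 the extreme is -0.72. The bias is 0 whenever the trend ends by week 10, and 0 for every T if weeks 10-12 and 30-32 are used in both groups.

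*All sensor weeks averaged.* The extreme is R = 20, T = 5.66:
- Group 1 CGM, weeks 0-12: (5.66 × 10 + 6.34 × 20)/12 = 15.28; its control weeks are at 20; difference -4.72.
- Group 2 control: weeks 0-4 average 20 × 2/5.66 = 7.07 and weeks 12-14 average 20, so (4 × 7.07 + 2 × 20)/6 = 11.38; its CGM weeks are at 20; difference +8.62.

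Mean: (-4.72 + 8.62)/2 = **+1.95**. Moving the closing sensor to weeks 10-12 changes nothing here, because the trend is already flat by then. Over the whole range the bias is about +0.1 to +1.95 as dated and +0.25 to +1.95 with the sensors moved.

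**Step 3: share of a real CGM effect recovered.** Model: weekly data, 15 per group, a random patient intercept (within-patient correlation 0.3 to 0.7, assumed) and one term per study week. Its bias with no CGM effect is 0 on every schedule. The effect is assumed to build linearly from zero at phase start to full size.

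| Time to full effect | Dated visits | Closing sensors at weeks 10 and 30 |
|---|---|---|
| Immediate | 100% | 100% |
| 2 weeks | 63% | 79% |
| 4 weeks | 38% | 65% |
| 8 weeks | 19% | 53% |
| 12 weeks | 13% | 46% |

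The choice of correlation moves these by less than one percentage point. As a rough check on the last row, the 12-week build-up averages 2/12 = 0.17 over weeks 0-4 and 1/12 = 0.08 over weeks 20-22, and the model's 0.13 lies between. For matched opening and closing fortnights the same build-up gives (1/12 + 11/12)/2 = 50%.

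**The case against.** The strongest reply is that the documents conflict less than they seem to. Beginning and end could mean fitted at the opening and closing visits, which matches Group 1's weeks 20 and 32. The heading for weeks 13-19 can be read as placing the week-12 visit in Phase I. The twelve-week wording may say who wears the sensor rather than that wear is continuous. All this is fair, but it does not reconcile the text: Group 2's extra week-2 fitting and the unscheduled weeks 18-20 remain. Nor does it fill the gap, since a sensor fitted at week 12 still records weeks 12-14.

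The Schedule of Events and the grant application are attached but not shown, and may name the operative schedule or the comparison weeks. That limits the point to the visible text. It cannot make the visible passages agree.

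Four stronger readings are tempting and are not supported:

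- **That control sensor data are lost.** The opening fortnights have masked data with concurrent Libre 2 data. The late windows still reflect glucometer management: this is explicit for Group 2, and nothing changes it for Group 1. Glucometer readings and routine labs also remain.
- **That the schedule conflict causes a bias of up to +1.95 points.** That figure comes from averaging unequal weeks, and its maximum is the same after the sensors are moved. Only the 0 to -1.44 range comes from the displaced closing windows.
- **That the dated schedule recovers only 13% of the effect.** That is the slowest build-up examined, and the documents give no build-up curve.
- **That the bias can be set against the 0.275 go threshold.** The plan does not say which standard deviation that effect size uses, or that criterion (b) rests on a sensor metric.

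**Conclusion.** The point stands as a schedule conflict with a conditional gap. The calendar result is firm: if the dated visits are followed, masked coverage of weeks 10-12 and 30-32 is 0 of 2 weeks in each group, and shared sensor weeks number 6 rather than 10. The gap does not arise under the narrative wording or under continuous wear.

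The statistical consequence is modest and rests on assumed trends. It is a bias of 0 to -1.44 points if closing windows are compared as dated, and a loss of recovered effect ranging from none (immediate effect) to 33 percentage points (46% - 13%, for a 12-week build-up) against the moved schedule. It concerns a secondary outcome. Feasibility and acceptance, the primary outcome, are not affected, and go criterion (b) is affected only if it uses a sensor metric. It should be fixed, because the pilot is meant to show that usable data can be collected for a larger trial.

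**What to change.** 1. Reconcile the Human Subjects section, the device section, the Methods narrative and the dated visits into one masked-sensor schedule, and make the Schedule of Events match.
2. Place the closing masked window inside the control phase, in line with the narrative and device sections. For example, fit it at the routine two-weekly clinic visits at week 10 (Group 2) and week 30 (Group 1).
3. State the weeks compared for time in range. Either use the same study weeks in both groups (0-2, 10-12, 20-22, 30-32), or use all sensor weeks with study week as a category.

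Steps 2 and 3 are both needed. Moving the sensors alone leaves the bias from averaging unequal weeks, and naming the analysis alone leaves only the early shared weeks.

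The cost is protocol wording and one short fitting per participant at a routine visit outside the five study visits, with the same number of sensors. With matched weeks, the other 8 of 12 Libre 2 weeks become descriptive. With study week as a category all weeks stay in the model, though weeks with sensors in only one group add little to the treatment contrast.
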